## 15.5 12-Lead Electrocardiogram (ECG)

The 12-lead ECG data will be listed and summarized for observed values, CFB and percent CFB values by treatment group using descriptive statistics:

- RR interval (ms)
- PR interval (ms)
- QRS (ms)
- QT (ms)
- Fridericia corrected QT (QTcF) (ms).

QTcF values will be categorized according to their calculated values into the categories

- $\leq 430$  ms,
- $> 430 - 450$  ms,
- $> 450 - 480$  ms,
- $> 480 - 500$  ms,
- $> 500$  ms

and categorized according to their CFB into the categories

- $\leq 30$  ms,
- $> 30 - 60$  ms,
- $> 60$  msec.

A listing of ECG quantitative values, morphological and rhythm results will be produced.

A shift table of rhythm results, from baseline to end of treatment, of the number and percentage of subjects for each category (Sinus rhythm, Atrial fibrillation, Other, Missing and Total) will be provided.

A shift table of morphological assessments, from baseline to worst on treatment observation of the 12-week treatment period, of the number and percentage of subjects for each interpretation category (Normal, Abnormal NCS, Abnormal CS, Missing, and Total) will also be provided.

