#### 3.4 Risk/Benefit

No identified risks or new potential risks have emerged from the completed Studies EMR200527-001 or MS200527-0019 in healthy volunteers or SLE Study EMR200527-002. No new safety signals have been confirmed from ongoing Study MS200527-0081 as of an IDMC data review meeting on 24 October 2017.

Important potential risks to subjects are based on nonclinical safety data of evobrutinib and clinical data on adverse drug effects associated with compounds of a similar pharmacological class. They include infection, leukopenia, thrombocytopenia, hemorrhage, gastrointestinal intolerance, renal toxicity, hepatocellular injury, atrial fibrillation, and embryo-fetal toxicity. The potential risk of infection relates to the immunomodulatory actions of evobrutinib. Women of childbearing potential participating in clinical studies with evobrutinib must agree to adhere to the use of highly effective contraception as specified in the clinical study protocol. CCI

Risk minimization measures routinely implemented in early phase clinical trials, including exclusion criteria for hematological cytopenias and stopping rules based on grade changes in specific laboratory parameters, are considered adequate for planned clinical trials in patients with autoimmune diseases. No additional risk minimization measures are proposed.

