#### 7.1.2.1 End of Treatment Visit

The End of Treatment Visit will be performed at Week 12 or within 5 days of early discontinuation of treatment with the IMP. Subjects will undergo assessments as described in [Table 1](#). In case of premature discontinuation, the PRO assessments have to be completed at the End of Treatment visit.

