#### 7.4.4.3 12-lead ECG and Chest X-ray

A single 12-lead ECG will be performed as indicated in [Table 1](#). The 12-lead ECG recordings will be obtained after 10 minutes of rest in a semisupine position. **CCI** blood sampling should be collected immediately following ECG assessment.

The following ECG parameters will be obtained from the computerized 12-lead ECG recordings: rhythm, heart rate (as measured by RR interval), PR interval, QRS duration, and QT interval. The corrected QT interval (QTcF) will be calculated using Fridericia's formula. The overall evaluation (normal/abnormal) will be recorded on the eCRF, and if abnormal, the specific abnormality will be recorded. Abnormal evaluations will be judged as clinically significant or not clinically significant by the Investigator.

The printout of the ECG is to be signed, dated, and filed in the Investigator's Site File along with a signed and dated copy (if the printouts are not on archive-quality paper). In addition, ECGs will also be stored digitally by the Sponsor.

Posteroanterior CXRs will be performed during Screening according to local standard practice. Subjects who had a CXR performed for clinical reasons within the last 3 months of Screening do not need to have the CXR repeated. The CXR should show no evidence of active infective process, or any other clinically significant abnormalities. The overall evaluation (normal/abnormal) will be recorded on the eCRF, and if abnormal, the specific abnormality will be recorded. Abnormal evaluations will be judged as clinically significant or not clinically significant by the Investigator.

The 12-lead ECG and CXR will be performed and read locally.

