**Table 46: Time Windows for ECG**

Treatment groups	Period covered	Interval (days) [Date of assessment – Date of first dose + 1]	Analysis Visit

 
• Placebo
 
• Evobrutinib 25 mg QD
 
• Evobrutinib 75 mg QD
 
• Evobrutinib 50 mg BID
 
	12-week treatment period	1	Day 1
		[ 2 ; 70 )	Week 8 – Day 56
		[ 70 ; 91 )	Week 12 – Day 84

 
• Placebo/Evobrutinib 50 mg BID
 
• Evobrutinib 25 mg QD/Evobrutinib 50 mg BID
 
• Evobrutinib 75 mg QD/Evobrutinib 50 mg BID
 
• Evobrutinib 50 mg BID/Evobrutinib 50 mg BID
 
	OLE period	1	Day 1 – OLE
		[2 ; 270 )	Month 6 – OLE
		[ 270 ; 367 )	Month 12 – OLE

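### The ECG rhythm shift table stops at end of treatment, so atrial fibrillation seen at Week 8 and gone by Week 12 is not counted by arm in the only visible ECG-based rhythm summary

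*SAP*

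**What the plan says.** SAP 15.5 defines two ECG shift tables in consecutive sentences.

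- Rhythm: "A shift table of rhythm results, from baseline to end of treatment, of the number and percentage of subjects for each category". The categories are given as "Sinus rhythm, Atrial fibrillation, Other, Missing and Total) will be provided".
- Morphology: the table runs "from baseline to worst on treatment observation of the 12-week treatment period".

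The same section adds: "A listing of ECG quantitative values, morphological and rhythm results will be produced". No other summary of rhythm is planned in the visible text.

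Protocol 3.4 includes atrial fibrillation among the important potential risks: "hepatocellular injury, atrial fibrillation, and embryo-fetal toxicity". Protocol 7.4.4.3 says that the ECG recordings supply "rhythm, heart rate (as measured by RR interval), PR interval, QRS duration, and QT interval", so rhythm is available from every ECG. Protocol Table 1 places ECGs at Screening, Day 1, Week 8 and the Week 12/End of Treatment/Early Withdrawal visit, and none at the Safety Follow-up Visit. Protocol 7.1.2.1 says: "The End of Treatment Visit will be performed at Week 12 or within 5 days of early discontinuation of treatment with the IMP".

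**The concern.** The rhythm table gives atrial fibrillation its own row and column, so its evident purpose is to show by arm how many subjects moved into that rhythm. Atrial fibrillation can be intermittent. A table that looks only at the last reading answers a narrower question: who was in atrial fibrillation when treatment ended. For a cardiac risk that the sponsor has itself named, the relevant count is who was in atrial fibrillation at any ECG on treatment. That is how the adjacent morphology table is built.

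At stake is the completeness of one descriptive safety table. No efficacy result or hypothesis test depends on it.

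**Working it through.** The plan gives no figure to reproduce. The check sets the table definition against the ECG schedule, the time windows and the other outputs.

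**1. Readings used.** Table 1 schedules two on-treatment ECGs, at Week 8 and at Week 12/End of Treatment. For a completer the rhythm table uses the second only, so 1 of 2 scheduled readings (50%) does not enter.

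**2. Where subjects fall.** SR is sinus rhythm and AF is atrial fibrillation. All five start in SR.

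| Subject | Week 8 | Week 12/End of Treatment | Table as planned | Worst on-treatment rule |
|---|---|---|---|---|
| A | SR | AF | SR to AF | SR to AF |
| B | AF | SR | SR to SR | SR to AF |
| C | AF | Other | SR to Other | SR to AF |
| D | AF | No ECG | SR to Missing | SR to AF |
| E (stops before Day 70) | None | AF at early-withdrawal ECG | Depends on programming (step 3) | SR to AF |

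Subjects B, C and D each had atrial fibrillation recorded on treatment, and none is counted under it. Only B is shown as sinus rhythm.

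**3. Early stoppers.** "Table 46: Time Windows for ECG" assigns Days 2 to 69 to Week 8 and Days 70 to 90 to Week 12, and has no visit labelled end of treatment. SAP 9.6 (Time windows) makes the analysis visit the basis for derivations and presentations. If end of treatment is programmed as the Week 12 analysis visit, subject E is Missing. If it is programmed as the protocol's End of Treatment visit, E is counted. The visible text does not settle which.

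**4. Other safety shift tables in the SAP.**

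- Laboratory (15.3): worst CTCAE grade after baseline.
- Vital signs (15.4): maximum change from baseline.
- ECG morphology (15.5): worst on treatment.
- HBV DNA (15.11): worst value after baseline.
- ECG rhythm (15.5): end of treatment only.

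Rhythm is the exception, and no reason is stated.

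**5. What the other outputs recover.**

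- The listing keeps the Week 8 rhythm but gives no count by arm.
- The morphology table may show the Week 8 ECG as abnormal, without identifying the rhythm.
- The TEAE tables (SAP 15.1.1.3, Table 25) count atrial fibrillation once it is reported as an adverse event. Protocol 7.4.1.1 makes an abnormal ECG finding reportable only if it comes with signs and symptoms, leads to stopping treatment, or is otherwise considered medically important by the investigator.

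What remains uncounted is atrial fibrillation that meets none of those three conditions and is absent from the end-of-treatment ECG.

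**The case against.** The strongest reply is that little is lost from the report as a whole. Symptomatic atrial fibrillation, or atrial fibrillation that ends treatment, is an adverse event under Protocol 7.4.1.1. It is then tabulated by arm across treatment and safety follow-up, whatever the ECG timing. Rhythm is not among the ECG parameters in the key secondary safety endpoints (Protocol 8.3.2), and Protocol 8.5.4.1 promises no rhythm shift table, so the SAP table is already an extra. Rhythm categories are nominal, so a worst value needs an added ranking. The Tier 1 list (SAP Appendix 18.10) and the detail on events of special interest (SAP 15.1.1.4) are not visible, and atrial fibrillation may be prespecified there.

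Most of this stands as a limit on weight. It does not remove the point. The hidden lists concern adverse events and would pass through the same reporting filter, so they would not supply an ECG-based count. The ranking takes one line to state. Being an extra table is no reason to build it on a narrower rule than the table next to it.

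Two further inferences are tempting and go beyond the text. A reader might infer that early stoppers are lost as well. That holds only under one reading of end of treatment, and Protocol 7.1.2.1 supports the other. A reader might also infer that every unscheduled ECG is ignored. The visible text does not mention unscheduled ECGs. Under Table 46 one on Days 70 to 90 would map to Week 12, although no visible rule chooses between several ECGs in one window.

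**Conclusion.** The point holds for the rhythm shift table. For completers it leaves out one of two scheduled on-treatment ECGs, and atrial fibrillation present at Week 8 but not at the end-of-treatment ECG is not counted by arm in the only ECG-based rhythm summary visible. This rests on reading end of treatment as a single final reading, which the contrast with the morphology sentence supports.

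The resulting gap in reporting is narrow: mainly transient, asymptomatic atrial fibrillation not judged medically important and not leading to discontinuation. Its size cannot be estimated. A reader might attach a percentage by assuming that each ECG catches an episode independently with probability q. The missed share is then 1 − q/(2q − q²) = 1 − 1/(2 − q), or 47% at q = 0.1, 41% at q = 0.3 and 33% at q = 0.5. Neither q nor independence has any basis in the documents, and the percentage would apply to an unknown and possibly very small count. Nor do the documents support saying that atrial fibrillation goes unreported, or that the table is biased toward any arm.

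The change is worth making before database lock because it is cheap and concerns a named risk.

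**What to change.** In SAP 15.5, give the rhythm shift table the same time rule as the morphology table: "from baseline to worst on treatment observation of the 12-week treatment period". Add two specifications:

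- Rank the categories as atrial fibrillation, then other, then sinus rhythm, with Missing only if no on-treatment ECG has a rhythm result.
- Use all on-treatment ECGs, stating that early-withdrawal and any unscheduled ECGs are included.

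The end-of-treatment column may be kept alongside. The new rule also removes the ambiguity over an early-withdrawal ECG before Day 70, because the analysis visit to which Table 46 assigns it no longer matters.

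The cost is one sentence in the SAP and a small programming change. The data are already collected and no trial procedure changes. The protocol does not specify this table, so no protocol amendment is needed.

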## 15.6 Physical Examination

No summary table will be provided since physical examination findings during screening will be recorded as medical history events and findings during the trial as AEs.

## 15.7 Pregnancy Test

Results of pregnancy test (serum and urine beta human chorionic gonadotropin for women only) will be listed.

## 15.8 Serum IgG, IgA, IgM Levels

Boxplot of Serum IgG, IgA and IgM levels (mg/dL) by treatment group and time point will be provided. Descriptive statistics by treatment group and time point will be performed as well. Serum IgG, IgA and IgM levels data will be listed by treatment group, subject and time point (where applicable).

## 15.9 B (CD19+) Cell Count

A boxplot of B (CD19+) cell count (cells/ $\mu$ L) by treatment group and time point will be provided. Descriptive statistics by treatment group and time point will be performed as well. B (CD19+) cell count data will be listed by treatment group, subject and time point (where applicable).

## 15.10 Urinalysis Microscopic Evaluation

Urinalysis Microscopic Evaluation data will be listed by treatment group and time point (where applicable). Parameters are listed in Appendix 18.8.

## 15.11 HBV DNA

Hepatitis B Virus (HBV) deoxyribonucleic acid (DNA) polymerase chain reaction (PCR) testing results will be listed by treatment group and time point (where applicable). A shift table from baseline to worst post-baseline values including the categories  $< 20$  IU/mL versus  $\geq 20$  IU/mL will be provided.

The logo for CCI (Clinical Care Innovations) is displayed in large, bold, red letters. The letters 'C', 'C', and 'I' are stacked vertically, with the 'C's on top and the 'I' on the bottom. The logo is set against a solid black rectangular background.

16

Analyses of Other Endpoints

CCI

CCI

CCI

CCI

## 18 Appendices

### 18.1 Definitions of Efficacy Endpoints

**ACR20** - The ACR20 is a primary efficacy measure for which a subject must have at least 20% improvement in the following ACR Core Set values:

- TJC (being the number of joints assessed as “Pain/Tender only” or “Pain/Tender and Swollen” among the 68-joint count) and
- SJC (being the sum of joints assessed as “Swollen only” or “Pain/Tender and Swollen” among the 66-joint count) and
- An improvement of at least 20% in at least 3 of the following 5 assessments:
  - Subject’s Global Assessment of Disease Activity
  - Subject’s Assessment of Pain
  - Subject’s Assessment of Physical Function as measured by the HAQ-DI
  - Physician’s Global Assessment of Disease Activity
  - Acute phase reactant as measured by hsCRP.

In this trial, ACR20 response calculations will use the HAQ-DI for the subject’s assessment of physical function and hsCRP as the measure of acute phase reactant.

Improvement of at least 20% of these assessments is defined as follows:

- TJC (68 joint count): a decrease of at least 20% of the number of tender joints compared to baseline
- SJC (66 joint count): a decrease of at least 20% of the number of swollen joints compared to baseline
- Subject's Global Assessment of Disease Activity: a decrease of at least 20% on the VAS compared to baseline. *Note: The scale has been scored from 100 [very well] to 0 [very poor] during the data collection. As a result, for analyses, the parameter is derived as 100 – the original value to correctly assess the subject's global assessment of disease activity and calculate the improvement from baseline.*
- Subject's Assessment of Pain: a decrease of at least 20% on the VAS compared to baseline.
- Subject's Assessment of Physical Function: a decrease of at least 20% of the HAQ-DI score compared to baseline.
- Physician's Global Assessment of Disease Activity: a decrease of at least 20% on the VAS compared to baseline
- Acute phase reactant: a decrease of at least 20% of hsCRP measurement compared to baseline

**ACR50, ACR70** - ACR50 and ACR70 are defined in the same way as the ACR20 using at least 50% and 70% improvement, respectively.

**DAS28-hsCRP** - The DAS28-hsCRP is a measure of disease activity in 28 joints that consists of a composite numerical score of the following variables: TJC, SJC, hsCRP, and Patient's Global Assessment of Disease Activity ([Vander Cruyssen 2005](#)).

For DAS28-hsCRP, the 28 joints to be examined and assessed as tender or not tender for TJC and to be examined and assessed as swollen or not swollen for SJC include 14 joints on each side of the subject's body: 2 shoulders, 2 elbows, 2 wrists, 10 MCP joints, 2 interphalangeal joints of the thumb, 8 proximal interphalangeal joints, and 2 knees ([Smolen 1995](#)).

In this trial, the acute phase reactant for computing DAS28 is the hsCRP. DAS28-hsCRP will be derived using the following formula from the DAS28 website ([DAS28 2016](#)):

$$DAS28-hsCRP = 0.56 \times \sqrt{(TJC28)} + 0.28 \times \sqrt{(SJC28)} + 0.014 \times GH + 0.36 \times \ln(hsCRP + 1) + 0.96$$

Where:

- TJC28 = 28 joint count for tenderness
- SJC28 = 28 joint count for swelling
- $\ln(hsCRP)$  = natural logarithm of hsCRP

GH = the general health component of the Disease Activity Score (DAS) (i.e., Patient's Global Assessment of Disease Activity).

**ACR Hybrid** - The ACR hybrid score was developed to provide a quasi-continuous score that can detect smaller changes between treatments than the categorical ACR20/50/70 scores by combining the continuous score of the mean improvement in the core set measures combining the ACR20, ACR50, and ACR70 scores with the mean percent change from Baseline in all 7 ACR response core set components (Felson 2007, American College of Rheumatology Clinical Trial Priorities and Design Conference 2010, van Vollenhoven 2011). ACR hybrid, along with the DAS28, is recommended by the FDA regulatory guidance as a way to support dose-response assessment. It is calculated according to Table 28:

**Table 28: Scoring Method for the Hybrid American College of Rheumatology Response Measure**

ACR Status	Mean % Change in Core Set Measures			
	< 20	≥ 20, < 50	≥ 50, < 70	≥ 70
Not ACR20	Mean % change	19.99	19.99	19.99
ACR20 but not ACR50	20	Mean % change	49.99	49.99
ACR50 but not ACR70	50	50	Mean % change	69.99
ACR70	70	70	70	Mean % change

Source: Felson 2007.

ACR = American College of Rheumatology, ACR20 = American College of Rheumatology 20% Response Criteria, ACR50 = American College of Rheumatology 50% Response Criteria, ACR70 = American College of Rheumatology 70% Response Criteria.

Note: 1) Calculate the average percentage change in core set measures. For each core set measure, subtract score after treatment from Baseline score and determine percentage improvement in each measure. Next, if a core set measure worsened by > 100%, limit that percentage change to 100% (a - 100% bound). Then average the percentage changes for all core set measures. 2) Determine whether the subject has achieved ACR20, ACR50, or ACR70. 3) Using the table above, obtain the Hybrid ACR response measure. To use the table, take the ACR20, ACR50, or ACR70 status of the subject (left column) and the mean percentage improvement in core set items; the Hybrid ACR score is where they intersect in the table.

**EULAR Responder index** – Assessments of subjects with RA by EULAR response criteria will be used to categorize subjects as having had no response, moderate response, good response, or any response (moderate + good responders) according to Table 29.

**Table 29: Categorization of Subject Responses as No Response, Moderate Response, or Good Response Based on EULAR Response Criteria**

Post-baseline Level of DAS28	Improvement Since Baseline in DAS28		
	> 1.2	≤ 1.2 and > 0.6	≤ 0.6
DAS28 ≤ 3.2	Good response	Moderate response	No response
3.2 < DAS28 ≤ 5.1			
DAS28 > 5.1			

Source: van Gestel 1996 and van Gestel 1998.

DAS28 = Disease Activity Score modified to include the 28 diarthrodial joint count.

**SDAI** – The SDAI is the numerical sum of 5 outcome parameters: TJC and SJC (based on a 28-joint assessment), the Patient’s and the Physician’s Global Assessments of disease activity (0–10 cm VAS), and level of CRP (expressed in units of mg/dL). The SDAI is a valid and sensitive assessment of disease activity (Aletaha 2005, Smolen 2014) and treatment response that is comparable with the DAS28 and ACR response criteria; it is easy to calculate and therefore a viable tool for day-to-day clinical assessment of RA treatment (Fransen 2005, Smolen 2014). The ACR/EULAR 2011 Index-based definition of remission is based on SDAI (SDAI ≤ 3.3), and is being assessed as a secondary endpoint (Felson 2011, Smolen 2014).

**CDAI** – The CDAI is a composite index (without acute-phase reactant) for assessing disease activity. CDAI is based on the simple summation of the count of SJC and TJC of 28 joints along with the Patient’s and Physician’s Global Assessments (0–10 cm VAS) for estimating disease activity. The greater advantage associated with CDAI is its potential to be employed in evaluation of subjects with RA consistently with close frequency and independently of any calculating device; therefore, it can essentially be used everywhere and anytime for disease activity assessment in subjects with RA (Aletaha 2005, Smolen 2014). Thresholds for disease severity grading are included in Anderson (Anderson 2012). Remission based on CDAI is also being assessed as a secondary endpoint.

**EULAR/ACR Boolean Remission** – Following the Boolean-based definition of remission of ACR/EULAR, at any time point, a subject must satisfy all of the following: tender joint count TJC ≤ 1, SJC ≤ 1, CRP ≤ 1 mg/dL and Patient’s Global Assessment ≤ 1 (on a 0–10 scale). The Patient’s Global Assessment must be elicited as follows: “Considering all of the ways your arthritis has affected you, how do you feel your arthritis is today? (0–10, where 0 = very well and 10 = very poorly)”. The Boolean criteria appear more stringent than the DAS28 remission and have been specifically created for use in clinical trials (Bykerk 2012, Felson 2011).

## 18.2 HAQ-DI Scoring

The HAQ-DI is a subject-reported questionnaire that consists of 24 questions referring to 8 domains: dressing and grooming, arising, eating, walking, hygiene, reach, grip, and activities.

The questionnaire scores the subject's self-perception (20 questions): 0=without any difficulty, 1=with some difficulty, 2=with much difficulty, 3=unable to do, and reports use of special aids or devices and/or the need for assistance from another person as indicated in [Table 30](#).

**Table 30: List of Questions from HAQ-DI Questionnaire**

Domains	Questions
Dressing and grooming	1. Dress yourself, including tying shoelaces and doing buttons? 2. Shampoo your hair?
Arising	3. Stand up from a straight chair? 4. Get in and out of bed?
Eating	5. Cut your meat? 6. Lift a full cup or glass to your mouth? 7. Open a new milk carton?
Walking	8. Walk outdoors on flat ground? 9. Climb up five steps?
	Check any aids or devices that you usually use for any of the above activities (questions 1 to 9): Devices used for dressing (button hook, zipper pull, etc.) / Special or built up chair / Built up or special utensils / Cane / Walker / Crutches / Wheelchair / Other
	Check any categories for which you usually need help from another person (questions 1 to 9): Dressing and grooming / Arising / Eating / Walking
Hygiene	10. Wash and dry your body? 11. Take a tub bath? 12. Get on and off the toilet?
Reach	13. Reach and get down a 5 pound object (such as a bag of sugar) from just above your head? 14. Bend down to pick up clothing from the floor?
Grip	15. Open car doors? 16. Open jars which have been previously opened? 17. Turn faucets on and off?
Activities	18. Run errands and shop? 19. Get in and out of a car? 20. Do chores such as vacuuming or yard work?
	Check any aids or devices that you usually use for any of the above activities(questions 10 to 20): Raised toilet seat / bathtub seat / bathtub bar / long-handled appliances in bathroom / long-handled appliances for reach / jar opener ( for jar previously opened) / Other
	Check any categories for which you usually need help from another person (questions 10 to 20): Hygiene / Reach / Gripping an opening things / Errands and Chores

The highest score for any component question of each of the eight domains determines the score for that domain. Each domain must have at least one question answered. Otherwise, the domain score is set to missing.

The non-missing domain scores are adjusted, based upon the patient’s use of any aid, device or assistance (multiple aids, devices, or assistance could be checked). The relationship between aids, devices help from another person and the disability domain is shown in [Table 31](#).

